4.4.2 Data Collection and Follow-up for Withdrawn Subjects

If a patient is terminated early from the study as a result of an adverse event, every effort will be made to follow the patient until the adverse event resolves.

5 Study Drug

5.1 Description

L-serine is a naturally-occurring, non-essential amino acid present in the human diet. L-serine will be presented in gummies containing 1g serine each. Gummies will be packaged into a foil package containing 2, 8, or 15 gummies with instructions to take one package in the morning and one in the evening, for a total of 4, 16, and 30g of L-serine/day, respectively. Placebo gummies containing no L-serine will be packaged in the same manner and given to patients to take two times a day.

5.2 Treatment Regimen

Participants will take the study drug or placebo in the form of gummies as described above. Subjects randomized into the L-serine arm will take 15 grams of L-Serine (15 gummies containing 1g of L-serine) orally twice daily for 246 days after the initial ascending dose period to confirm tolerability of the dose. Participants will be given three boxes of gummies to take home at each study visit. If the participant is unable to attend the study visit within the date range for the

scheduled visit the three boxes of gummies may be shipped to the participant. Email or phone contact from the participant confirming receipt of the study medication is required. Each box will weigh approximately five pounds and contain thirty days (60 packets) of gummies. During the initial period of accelerating doses, the gummies will be grouped and labeled into packages containing weeks one and two and weeks three and four respectively.

5.3 Method for Assigning Subjects to Treatment Groups

Participants will be randomized using an urn randomization procedure to ensure equal numbers of patients in both the placebo and L-serine groups receive either Placebo gummies or L-Serine gummies.

Foil packets will be pre-numbered with a lot number and then boxed by the manufacturer prior to shipment and delivery to DHMC. Boxes will contain either 60 packets of L-serine gummies or 60 packets of placebo gummies exclusively. The manufacturer will randomly assign kit numbers 1 through 40 to be used for either the L-serine arm or the placebo arm, with 20 kit numbers associated with each arm. Boxes will be labeled with a kit number corresponding to the correct arm, L-serine or placebo. Each kit number will be assigned to 9 boxes, the total number to be given to the subject. Randomization of the kit numbers and labeling of the corresponding boxes will take place at the manufacturer prior to being shipped to the study site. Patients will be assigned randomized kits in order of numbers 1-40 as they are consented into the study by study coordinators at DHMC.

The Investigational Pharmacy at DHMC, which does not have patient contact in the study, will have access to a sealed envelope which will contain the numbered box randomization key if necessary in an emergency unblinding scenario. The participants and DHMC study team will be unaware of the L-serine or placebo assignment.

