3.1 General Design

This is a Phase IIa, randomized, double-blind, placebo controlled trial. Potential subjects for participation in this study will be identified by the Investigator based on their clinical and radiographic diagnosis of Alzheimer's disease, which will be completed as part of standard care. Up to 40 subjects will be enrolled. Subjects participating in the study will be randomized to receive either gummies containing L-Serine or placebo gummies, with the Investigator and study staff blinded to the group assignments. An individual subject's participation in the study will last approximately 40 weeks from time of enrollment. Study office visits will take place at Day 0, week 12, week 24 and week 36. Phone contact will be made at week 2, week 4 and week 8 to assess compliance, adverse events and concomitant medication. A follow-up phone call will also be made at week 40 to inquire about adverse events, concomitant medication, subject impression of study, subjective L-serine tolerability, and if they are continuing L-serine supplementation. If, due to study-related events, the PI judges that a participant should be seen in office during study participation, a visit will be scheduled (Unscheduled Visit)

The Day 0 visit includes subject consent, administration and scoring of the Clinical Dementia Rating Scale, review of medical history including any family history of Alzheimer's disease, a brief neurological and physical exam, capture and grading of baseline conditions, and a review of concomitant medications. Hemoglobin A1C, safety labs (CBC, BMP) and research only blood draw will be completed. Eligibility will be confirmed by the PI prior to randomization. If a participant fails to qualify based on their CDR score or Hgb A1 level, the portion of their blood drawn for research only will be discarded.

All subsequent study visits include a brief physical/neurological exam, adverse event assessment, study medication compliance assessment, concomitant medications review, safety blood draws (CBC, BMP) and research-specific blood draws.

Study medication will be dispensed at Day 0, week 12, and week 24, and collected at week 12, week 24 and week 36. All unused study drug will be collected and returned to the study sponsor.

The MoCA will be performed at Visits 0, week 24, week 36, and at early withdrawal or unscheduled visits. Three different MoCA versions will be administered in a random order during these assessments.

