6.1 Visit 1: Screening and Enrollment (Day 0)

- Obtain Informed Consent
- Clinical Dementia Rating Scale
- Brief review of medical history and demographic collection
- Neurological and physical exam
- Capture and grade baseline conditions
- Concomitant medication assessment
- Montreal Cognitive Assessment (MoCA)
- Blood Draw:
 - Safety Labs completed locally (BMP, CBC)
 - Hemoglobin A1C level
 - Samples sent to the Brain Chemistry Laboratories for L-serine levels and neurally-derived exosomes with optional excess blood set aside for future protein expression and RNA blueprints
- Review of Inclusion/Exclusion Criteria
- Randomization
- Dispense study medication, dosing instructions and calendar

6.2 Follow-Up Phone Call #1: Week 2

- Medication Compliance
- Adverse Events
- Concomitant Medications

6.3 Follow-Up Phone Call #2: Week 4

- Medication Compliance
- Adverse Events
- Concomitant Medications

6.4 Follow-Up Phone Call #3: Week 8

- Medication Compliance
- Adverse Events
- Concomitant Medications

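### Does Section 5.3 randomize patients at consent, before their eligibility is known?

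*Combined protocol and SAP*

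**What the plan says.** Three sections bear on when a patient is allocated.

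- **Section 5.3** describes the mechanism. The manufacturer assigns kit numbers 1 to 40 to the arms at random, "with 20 kit numbers associated with each arm". On supply: "Each kit number will be assigned to 9 boxes, the total number to be given to the subject". On assignment at the site: "Patients will be assigned randomized kits in order of numbers 1-40 as they are consented into the study by study coordinators at DHMC".
- **Section 3.1** gives the order of events: "Eligibility will be confirmed by the PI prior to randomization". The next sentence begins "If a participant fails to qualify based on their CDR score or Hgb A1 level" and says what happens to that person's research blood, so failures after consent are foreseen. The size of the trial is given as a ceiling: "Up to 40 subjects will be enrolled".
- **Section 6.1** lists the Day 0 procedures. Consent comes first, the CDR and the blood draw with hemoglobin A1C follow, then "Review of Inclusion/Exclusion Criteria", then randomization, then dispensing.

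Section 5.8 adds that the kit number is also the subject number and that 40 unblinding envelopes are supplied. Section 7.3 limits the analysis to randomized subjects who took at least one dose.

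**The concern.** Sections 5.3 and 3.1 name different triggers for the same act. Section 10 requires consent before any study procedure, so the CDR score and the A1C result cannot be available at the moment of consent. A coordinator working from 5.3 alone could therefore hand the next kit number to someone who later proves ineligible.

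The supply has no visible slack: 40 kits for at most 40 patients, no spare kit mentioned, and no rule for a kit that is assigned but not dispensed. If such kits were written off, fewer than 40 eligible patients could be treated. The arms could also end unequal, although 5.3 describes an "urn randomization procedure to ensure equal numbers of patients in both the placebo and L-serine groups". A person allocated at consent and never dosed would count as randomized but fall outside the Section 7.3 analysis set.

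**Working it through.** **Reading the sections together**

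1. Section 3.1 is an explicit rule about timing: eligibility first, randomization second. It also provides for patients who fail after consent, and mentions only the disposal of their research blood.
2. Section 6.1 agrees with it. The list is not expressly labelled as sequential, so it is supporting evidence, and 3.1 carries the weight.
3. The sentence in 5.3 does two things that no other section does: it fixes the sequence (1 to 40) and says who assigns the kits. Taking its reference to consent as meaning enrolled makes all three sections agree. Taking it literally makes 5.3 contradict both of the others.
4. Dispensing comes last in 6.1. Even a kit number assigned too early would normally still be nine unopened boxes when the patient failed screening. No section says that such a kit is used up.

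**What a lost kit would cost**

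Inputs from Section 7.1: MoCA standard deviation 4, 20 patients per arm, detectable difference 3.65 points. Assumptions: two-sided alpha of 0.05 (the protocol does not state sidedness) and power 0.80 (Section 7.1 states this for the exosome measure, and I take it to apply to MoCA).

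For a two-sample t-test, the noncentrality is δ / [σ √(1/n₁ + 1/n₂)], and power is the probability that the noncentral t exceeds the 0.975 critical value on n₁ + n₂ − 2 degrees of freedom.

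*The protocol's own figure.* At 20 and 20: 3.65 / [4 √(1/20 + 1/20)] = 3.65 / 1.265 = 2.886, critical value 2.024, power 0.803. The difference detectable at power 0.80 is 3.64 points, which agrees with the stated 3.65.

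*Kits lost.* The documents give no screen-failure rate, so the number lost is assumed. Power is averaged over the possible splits when kits are lost at random from 20 and 20.

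| Kits lost | Patients left | Power at 3.65 points |
|---|---|---|
| 0 | 40 | 0.803 |
| 1 | 39 | 0.792 |
| 2 | 38 | 0.781 |
| 4 | 36 | 0.757 |

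The cost is about 0.01 per kit: 0.803 − 0.792 = 0.011 for the first, and (0.803 − 0.757) / 4 = 0.0115 on average over four.

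*Unequal arms.* With two kits lost, power is 0.781 at 19 and 19 and 0.780 at 20 and 18. With four lost, it is 0.758 at 18 and 18 and 0.753 at the most extreme split, 20 and 16. The total number matters; the split hardly does.

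**Bias**

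Under 5.3 the site team does not know which arm a kit belongs to. Whether a patient fails on CDR or A1C therefore cannot depend on the arm, and neither can the loss of a kit. Undosed patients are outside the Section 7.3 set in either arm.

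**The case for a change.** The strongest case for a change is practical. A coordinator carrying out allocation would turn to 5.3, because that is the section on allocation, and it names the wrong moment. Using the kit number as the subject number (5.8) makes numbering people at consent a natural habit. The loss need not be trivial either: if 20% or 30% of 40 consented patients failed and no kit were reused, 8 or 12 kits would go, and t-test power would fall to 0.70 or 0.64. Correcting the wording would take a sentence.

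The wording mismatch stands. So does the silence about a kit assigned but not dispensed, although that gap opens only if 3.1 has already been breached.

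The consequence does not stand. It needs three things together: staff acting on one clause of 5.3 against an express rule in 3.1, screen failures at an assumed rate, and unopened kits being discarded, which no section requires. The 20% and 30% figures are assumptions pushed through all three steps. Unequal arms add almost nothing, as the figures above show, and Section 7.1 already expects dropout, which reduces numbers and disturbs balance in the same way. Section 3.1 sets 40 as a ceiling, so a slightly smaller trial stays within the plan.

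**Conclusion.** The point is a clerical slip, and no change to the plan follows. Section 3.1 already requires confirmed eligibility before randomization, Section 6.1 is consistent with that order, and 5.3 can be read in line with both. Aligning the phrase in 5.3 would be harmless editing, but it would not alter what the trial does under its stated rule or what it can conclude.

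If 3.1 is followed, the effect is nil. If it is not, and undispensed kits are not reused, the cost is about 0.01 of power per kit against a starting value of 0.80, with no bias between arms. These figures rest on the protocol's SD of 4 and difference of 3.65 points, a two-sided t-test at 0.05, no dropout, and an assumed number of lost kits. The planned Mann-Whitney test would start slightly lower, but that comes from the choice of test and not from how kits are assigned.

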5.4 Preparation and Administration of Study Drug

L-serine and placebo preparation will be produced in a GMP compliant facility by Knechtel Laboratories, Inc. ([name]). The dose will be placed in sealed foil packages. Foil packages sufficient for 3 months will be given to the patients at each visit. Doses will be sent to Dartmouth Hitchcock Medical Center at the beginning of the study.

5.5 Subject Compliance Monitoring

Participants will be given study drug diaries and reminder sheets to attach to their wall/refrigerator in order to improve compliance and provide assistance to study staff in compliance monitoring. Participants will be asked to bring their drug diaries with them at each in person study visit for the study coordinator to review and log reported compliance into the CRF. Written instructions on how to take the medication and what to save and return will also be issued with each medication dispensation.

5.6 Prior and Concomitant Therapy

There are no prohibited concomitant medications. Participants are discouraged from taking any additional L-Serine supplementation as there is not any research to show the effects of higher dosing of L-serine. As part of the patient's history intake, concomitant medications will be recorded and then reviewed at each study visit. Patients must be on a stable dose of NMDA receptor antagonist medications or acetylcholinesterase inhibitor medication for at least 30 days prior to enrolling in the study and taking their first dose of study drug.

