1.2 Investigational Agent

L-serine (C₃H₇NO₃; 105.09 g/mol; synonym (S)-2-amino-3-hydroxypropanoic acid) is a naturally-occurring dietary amino acid. It is abundant in soy products, some edible seaweeds, sweet potatoes, eggs, and meat. Since some L-serine is produced by astrocytes in the brain, it is considered a non-essential amino acid. L-serine is directly involved in the biosynthesis of purines, pyrimidines, and other amino acids. Serine residues are found in most proteins and within proteins functions as a site for phosphorylation.

L-serine is considered as GRAS (generally recognized as safe) by the FDA and has been approved as a normal food additive under CFR172.320. It is widely sold as a dietary supplement. An FDA-approved Phase I human clinical trial of L-serine for ALS patients, sponsored by the Institute for Ethnomedicine and conducted by the Phoenix Neurological Associates, has now been published (Levine et al. 2016); patients were found to tolerate well doses up to 30 grams/day (ClinicalTrials.gov identifier NCT01835782). Similarly, Harvard University and Massachusetts General Hospital are conducting a two-year study on L-serine supplementation to correct biochemistry associated with hereditary sensory neuropathy type 1 at doses of 400mg/kg/day which for an average

American of 75.5kg is about 30 grams, the dose which we propose to use in this study (ClinicalTrials.gov identifier NCT01733407).

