3.4. Primary Safety Endpoint

Patients will be asked to report on the tolerability of the gummies. Safety labs will be drawn at baseline and at subsequent study visits to monitor for any adverse effects. These labs include CBC, BMP, and LFT's which will allow the Investigator to screen for any baseline blood values that could be considered clinically significant prior to study entry, and then continue to monitor throughout the trial. Additional blood from the draw will be sent to the Institute of Ethnomedicine to be tested for the amount of L-serine present.

4 Subject Selection and Withdrawal

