6.7 Visit 4: Week 36 (+/- 2 weeks)

- Brief neurological and physical exam
- MoCA exam
- Review of adverse events
- Review current medications
- Blood draw: Safety Labs completed locally and samples sent to the Brain Chemistry Laboratories for L-Serine levels and neurally-derived

exosomes with optional excess blood set aside for future protein expression and RNA blueprints

- Collect unused study medication and calendar. If participant unable to do this in person due to restrictions in place, provisions will be made to assist participant to mail the study medication and calendar to the research team at no expense to the participant.

6.8 Follow-Up Study Coordinator Phone Call: 4 weeks (+/- 2 weeks) after Visit 4:

- Review of adverse events
- Continued supplementation status
- L-Serine Tolerability
- Overall study impression

At study conclusion, the data will be collected and analyzed. Unblinding of study participants will occur after final analysis of all data.

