6.9 Blood Draws and Specimen Processing, Storage and Shipment

Safety labs will be drawn at four time points: Visit 1 (Baseline/enrollment), Visit 2, Visit 3 and Visit 4. Blood draws may be delayed and obtained at a later date (next in person visit due to restrictions placed on participant in person visits by Dartmouth-Hitchcock or the participant).

Safety labs include:

- Complete Blood Count
- Liver Function Test
- Basic Metabolic Panel

Blood samples will be drawn and sent to the Brain Chemistry Laboratories for analysis of L-Serine levels and neurally-derived exosomes at four time points: Visit 1 (Baseline/enrollment), Visit 2, Visit 3 and Visit 4 which may include delays in obtaining due to participant unable to attend the visit at the scheduled date

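### Off-study L-serine is only discouraged, for a reason that overlooks the placebo arm, and no use of the plasma L-serine levels is planned to detect it

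*Combined protocol and SAP*

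**What the plan says.** Section 5.6 opens with "There are no prohibited concomitant medications" and then says: "Participants are discouraged from taking any additional L-Serine supplementation as there is not any research to show the effects of higher dosing of L-serine". Section 1.2 says of L-serine: "It is widely sold as a dietary supplement". The eligibility criteria in 4.1 and 4.2 do not mention prior or current L-serine use. Section 4.4, by contrast, asks participants not to start NMDA receptor antagonists or acetylcholinesterase inhibitors during the trial, and withdraws those who choose to start.

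Two sources of information on off-study use already exist. Section 5.6 says that "concomitant medications will be recorded and then reviewed at each study visit", and sections 6.2 to 6.7 and the visit grid place a medication check at every call and visit through week 36. Section 6.9 schedules "analysis of L-Serine levels and neurally-derived exosomes at four time points: Visit 1 (Baseline/enrollment), Visit 2, Visit 3 and Visit 4". Section 3.4 introduces the L-serine assay under the safety endpoint: "Additional blood from the draw will be sent to the Institute of Ethnomedicine to be tested for the amount of L-serine present".

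The only contact that names L-serine supplementation is the week 40 call. Section 3.1 lists "subjective L-serine tolerability, and if they are continuing L-serine supplementation" among its topics, and section 6.8 lists "Continued supplementation status".

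Sections 7.1 to 7.3 mention neither off-study L-serine nor the plasma levels. The analysis population is everyone randomised who took at least one dose.

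**The concern.** The trial tests L-serine against no added L-serine. A placebo participant who buys the supplement receives some of the active agent, yet has broken no rule and simply counts as placebo. If L-serine works, this moves the placebo arm toward the active arm, so the bias in week 36 MoCA, in the MoCA slopes and in the exosome comparisons is toward no difference.

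The reason given in 5.6 fits an active-arm participant who adds to the study dose. It gives a participant who suspects placebo no reason to abstain. Section 4.4 shows that the protocol can set a firmer rule where a therapy might disturb the cognitive outcome; the test agent has no such rule. The week 40 question also suggests that outside access was foreseen: unused study product is due back at Visit 4, so a participant still supplementing at week 40 would ordinarily be using a non-study source. By then the primary endpoint has been measured.

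With 20 per arm, one placebo participant is 5% of the arm, and the sample-size section makes no allowance for contamination.

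**Working it through.** **Inputs.** From section 7.1: MoCA SD 4, 20 per arm, minimum detectable difference 3.65 points; exosomal beta-amyloid SD 2.8 pg/ml, detectable difference 2.5 pg/ml. Power 0.8 and alpha 0.05 are stated there for the biomarker and assumed to apply to MoCA. Two-sided testing follows from the alternative hypothesis in 7.2. The contamination fraction f is not in the documents and is varied.

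**Step 1: reproduce the plan's figure.** Standard error of the difference = 4 × √(2/20) = 1.265. Noncentrality at 3.65 points = 3.65 / 1.265 = 2.886. With 38 degrees of freedom the two-sided 0.05 critical value is 2.024, and the noncentral t gives power 0.803. The difference giving exactly 80% power is 3.64 points, so the stated 3.65 reproduces. A one-sided test would give 3.20, which does not match.

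**Step 2: dilute the contrast.** If a fraction f of the placebo arm gets the full active effect, the expected difference is 3.65 × (1 − f). For the biomarker it is 2.5 × (1 − f).

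| f (placebo participants of 20) | MoCA difference | Noncentrality | MoCA power | Biomarker power |
|---|---|---|---|---|
| 0 | 3.65 | 2.886 | 0.803 | 0.786 |
| 5% (1) | 3.47 | 2.741 | 0.762 | 0.743 |
| 10% (2) | 3.29 | 2.597 | 0.716 | 0.697 |
| 20% (4) | 2.92 | 2.308 | 0.614 | 0.595 |

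To keep 80% power for MoCA, the true full effect would have to be 3.64 / (1 − f): 3.83, 4.04 and 4.55 points.

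**Step 3: how far the table depends on its assumptions.** It gives every contaminated person the full effect of the study regimen. If each gets half, f counts half: 10% contamination gives 3.65 × (1 − 0.10 × 0.5) = 3.47 points and power 0.76, the 5% row. In the other direction, the table ignores the extra spread in a mixed placebo arm, f(1 − f) × 3.65². At 20% this is 0.16 × 13.32 = 2.13 added to a placebo variance of 16; the average of the two arms' variances becomes 17.07 (SD 4.13) and power 0.59 instead of 0.61. At 5% and 10% the same step gives 0.75 and 0.70. The table uses a t-test, whereas the planned test is Mann-Whitney, and 3.65 is a detectable difference, not a forecast effect.

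**Step 4: match the data collected to the use planned.** Section 6.9 provides one baseline and three later plasma L-serine samples per participant. Section 7 gives no threshold, comparison or reporting rule for them. The medication reviews name neither supplements nor L-serine, so a product sold as a dietary supplement may go unreported.

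**The case against.** The strongest reply is that the means of detection are already in place. Medications are checked at every contact, and plasma L-serine is measured four times. A reader might infer from section 5.6 that, after a null result, the trial could never tell contamination from lack of effect. The documents do not support that: the samples exist and could be examined. What stands is narrower, namely that no use of them is prespecified.

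A reader might also infer that the placebo arm is left uncovered, or that the protocol restricts no therapy at all. Neither is right. The instruction in 5.6 is addressed to participants generally, and under blinding placebo participants receive it too; section 4.4 does restrict starting two drug classes.

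It can fairly be said that a firmer rule would rest on the same self-report and blood data, and that the documents do not show it would reduce use. That is true. The wording alone may change little, so the naming of L-serine at each contact and the prespecified use of plasma levels matter at least as much.

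Plasma levels are also an imperfect marker. Section 1.1 puts ordinary intake at 3.5 g/day, and no fasting state or time since last dose is specified for the draws. A raised level therefore has no definition yet, which is a reason to define it in advance relative to the participant's own baseline.

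Finally, this is a 40-patient proof-of-concept study seeking preliminary indications of efficacy, and the risk is hypothetical. That limits the weight of the point, but the remedy is small.

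**Conclusion.** The point holds. As written, the plan lets a placebo participant take the test agent without breaching any requirement, and it does not say how this would be recognised or reported. The direction of bias, if L-serine has an effect, is toward no difference.

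The size is conditional. For a true 3.65-point effect, SD 4 and 20 per arm, power falls from 80% to 76%, 72% or 61% at 5%, 10% or 20% contamination. This is the worst case per contaminated person under a simple dilution model, apart from the small extra variance shown above. Nothing in the documents supports a particular rate, dose or duration of off-study use, so a reader should not infer that contamination will occur or that any row of the table is the expected power.

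**What to change.** 1. Reword section 5.6 so that avoiding non-study L-serine until the Visit 4 MoCA and blood draw are complete is a trial-conduct requirement in both arms, with protection of the treatment contrast given as the reason. State that anyone who takes it remains in follow-up and in the as-randomised primary analysis.
2. At the medication check already made at each call and visit, ask about L-serine supplements by name and record the answer on the CRF.
3. Before unblinding, prespecify how reported use and change in plasma L-serine from the participant's own Visit 1 level will identify likely off-study use. Fix the rule before its authors see post-baseline levels, since these may reveal the arm. After unblinding, report the number of placebo participants identified, as a measure of the treatment contrast achieved.
4. Prespecify any supportive analysis so that it keeps the randomised comparison, for example a contamination-adjusted estimate with randomisation as the instrument. In the simple model above with f = 10%, dividing the as-randomised difference by the difference in exposure gives 3.285 / (1 − 0.10) = 3.65; this corrects the estimate but does not restore the lost power. Do not exclude only the placebo participants with high levels: that one-arm, post-randomisation exclusion would itself bias the comparison.

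The cost is a short amendment, one CRF question and one supportive analysis of samples already scheduled. A few candidates unwilling to forgo the supplement may decline. No study dose, visit or blood draw changes.
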